10 PROTOCOL DEVIATIONS

Critical protocol deviations will be identified prior to database lock for final analysis and will be listed and summarized.

11 EFFICACY ANALYSES

Disease activity will be assessed by the study investigators by using CBC and peripheral blood cell morphological examination, examination of bone marrow aspiration (or biopsy if required), and physical examination. Modifications to the Revised Recommendations of the International Working Group for Diagnosis (IWG), Standardization of Response Criteria, Treatment Outcomes, and Reporting Standards for Therapeutic Trials in Acute Myeloid Leukemia will be used (**Appendix 1**). Response assessment will be based on bone marrow aspirate/biopsy and the best CBC up to 14 days post bone marrow aspirate/biopsy. Responses will be categorized as:

- CR: mCR (morphologic CR], CRc (cytogenic CR], or CRm (molecular CR);
- CRh (CR with partial hematologic recovery);
- CRi (CR with incomplete blood count recovery): CRn (CR with incomplete neutrophil recovery) or CRp (CR with incomplete platelet recovery);
- MLFS (morphologic leukemia free state);
- PR (partial response);
- OB (other benefit);
- SD (stable disease);
- PD (progressive disease).

The number and percent of PIF/ER AML patients will be summarized by best overall response. Efficacy analyses will be based on the PIF/ER AML population

. All efficacy results will be summarized by PIF, ER and the total combined PIF/ER populations.

11.1 Primary Efficacy Analysis

The primary efficacy endpoint for the AML expansion cohort is the CR/CRh rate, calculated as the proportion of patients in the efficacy population that has achieved a best response of CR (mCR, CRc, or CRm) or CRh at any point during treatment by investigator's assessment, according to IWG AML response criteria (Appendix 1). CR/CRh rate will be summarized for total combined PIF/ER patients as the primary analysis, as well as for PIF and ER patients, separately, and for PIF/ER patients in the response evaluable population as a sensitivity analysis. A two-sided exact 95% confidence interval will be calculated around response rates.

For the second interim analysis of 100 patients, as well as for the final analysis of 170 patients, all treated patients will be followed for at least 6 months or death from any cause, whichever comes first, prior to data cut off for the analysis. If the trial passes the pre-specified efficacy boundary (25% observed CR/CRh rate) at the second interim analysis, a two-sided exact 95% confidence interval described by Jennison and Turnbull (44) will be produced to account for the bias in the conventional exact confidence interval for fixed sample test.

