# 9.6.1 Primary Efficacy Analysis

The primary efficacy endpoint for the AML expansion cohort is the CR/CRh rate, calculated as the proportion of patients in the efficacy population that has achieved a best response of CR (mCR, CRc, or CRm) or CRh at any point during treatment by investigator's assessment, according to IWG AML response criteria (Appendix 3). CR/CRh rate will be summarized for the total combined PIF/ER patients as the primary analysis, as well as for PIF and ER patients separately, and for PIF/ER patients in the response-evaluable population as a sensitivity analyses. A two-sided exact 95% confidence interval will be calculated around response rates.

For the second interim analysis of 100 patients, as well as for the final analysis of 170 patients, all treated patients will be followed for at least 6 months or until death from any cause, whichever occurs first, prior to data cutoff for the analysis. If the trial passes the prespecified efficacy boundary (25% observed CR/CRh rate) at the second interim analysis, a two-sided exact 95% confidence interval as described by Jennison and Turnbull (21) will be produced to account for the bias in the conventional exact confidence interval for fixed sample test.

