4.2 Sample Size Determination

The planned sample size for the pivotal portion of the study as of Protocol Amendment 11 is 170 patients, based on a three-stage design.

To determine the sample size under inclusion criteria, historical reference response rates to standard treatments were ascertained through a meta-analysis based on 5 published studies that included PIF/ER AML patients selected from 963 publications identified through database search (1; 2; 3; 6; 7). The response rate identified by the meta-analysis is based on a random intercept logistic regression model, yielding a combined CR/CRh rate for PIF/ ER AML of 11.8%, with a 95% confidence interval of 9.4% to 14.7% (Figure 1).

Figure 1 Forest Plot for Meta-analysis

Study	Events	Total		Proportion 95%-CI
1, CLASSIC I (FaderI JCO 2012) 2, VALOR (Ravandi Lancet Oncol 2015), Refractory 3, VALOR (Ravandi Lancet Oncol 2015), Early Relapse 4, Admiral (Gilteritinib), Chemo 5, Anti CD33 ADC Gemtuzumab, Phase I 6, Anti CD33 ADC Gemtuzumab, Phase II 7, Venetoclax w/ HMA,or LDAC(2) MDACC, Di Nardo	15 16 13 2 4 2	83 149 129 124 14 36 43		0.181 [0.105; 0.280] 0.107 [0.063; 0.169] 0.124 [0.073; 0.194] 0.105 [0.057; 0.173] - 0.143 [0.018; 0.428] 0.111 [0.031; 0.261] 0.047 [0.006; 0.158]
Fixed effect model Random effects model Heterogeneity: $I^2 = 0\%$, $\tau^2 = 0$, $p = 0.49$		578	0.1 0.2 0.3 0.4	0.118 [0.094; 0.147] 0.118 [0.094; 0.147]

The result obtained with the Bayesian method is consistent with the result of the random intercept logistic regression model (Table 1).

Assumption	Point Estimate	95% Credible Intervals (Highest Posterior Density)	95% Credible Intervals (Equal-tail)
Normal prior, normal (0, var=10000)	11.7%	(9.3%, 14.7%)	(9.2%, 14.6%)
Beta prior, beta (1, 1)	11.9%	(9.4%, 14.6%)	(9.4%, 14.7%)

Table 1Meta-analysis Using Bayesian Method

The upper 95% CI of 14.7% was chosen as the rate for the null hypothesis (H0) and a target of 23% CR/CRh was established as a clinically meaningful endpoint in this patient population.

A three-stage design with two interim analyses was employed to test the null hypothesis (H0) of CR/CRh rate = 14.7% against the alternative hypothesis (H1) of CR/CRh rate = 23%. Demonstration of CR/CRh rate improvement (H1) by rejecting H0 at a 1-sided type I error of 0.025 with adequate power (80%) in a sequential design requires 170 patients. Specifically, the planned number of patients and the futility and efficacy boundaries at each stage are as follows:

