- a. **First interim analysis:** The first interim analysis will be performed after 40 patients have been enrolled and either have had their responses evaluated or were discontinued for any reason from study treatment prior to their first response assessments. This interim analysis is for futility only, that is, the study enrollment will continue if at least 5 (12.5%) out of 40 patients have response of CR/CRh.
- b. Second interim analysis: If the enrollment continues after the first interim analysis, a second interim analysis will be performed after additional 60 patients have been enrolled (100 patients in total) and either have had their response evaluated or were discontinued for any reason from study treatment prior to their first response assessment. This interim analysis is for both futility and efficacy. Specifically,
 - i. If the number of CR/CRh is less than 15 (15%) out of 100 patients, then the study is considered futile and enrollment will be stopped.
 - ii. If the number of CR/CRh is 15 (15%) or greater out of 100 patients, then enrollment will continue.

- iii. If the number of CR/CRh is 25 (25%) or greater out of 100 patients, then H0 is rejected and the study is considered positive. The enrollment will still continue.
- c. **Final analysis:** If enrollment continues after the second interim, then the final analysis will be performed after additional 70 patients have been enrolled (170 patients in total) and either have had their response evaluated or were discontinued for any reason from study treatment prior to their first response assessments. If the number of CR/CRh is at least 35 (20.6%) out of the total of 170 patients, then H0 is rejected and the study is considered positive.

The above design yields a 1-sided alpha of 0.005 for the efficacy boundary at the second interim analysis and an overall 1-sided alpha of 0.024 with approximately 80% power at the final analysis (**Table 2**). The probability of early termination under H0 (futility) in the first two stages is 55%.

CP-MGD006-01: Statistical Analysis Plan

MacroGenics, Inc. Version 3.0, 19 April 2021

Table 2	Three Stage Design
---------	--------------------

H0 (Benchmark CR/CRh rate)	H1 (Target CR/CRh rate)	Stage 1			Stage 2		Efficacy interim analysis at the end of Stage 2		1-Sided alpha for rejecting H0	Power under H1			

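### The sequential exact 95% interval is planned only after an interim success, where it changes little; the final-analysis and second-interim futility intervals ignore the earlier looks

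*SAP*

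**What the plan says.** SAP 11.1 sets one default for the primary endpoint: "A two-sided exact 95% confidence interval will be calculated around response rates". Protocol 9.6.1 says the same. Both then make a single exception. In the protocol's words, "If the trial passes the prespecified efficacy boundary (25% observed CR/CRh rate) at the second interim analysis", a two-sided exact 95% interval taken from a group-sequential textbook is produced; the SAP explains that it "will be produced to account for the bias in the conventional exact confidence interval for fixed sample test".

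No sequential interval is planned for a final analysis at 170 patients without an interim crossing, or for a futility stop at 40 or 100. Neither document states how outcomes from different stages are to be ordered, and an exact sequential interval depends on that choice.

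If 25 or more of 100 respond, SAP 4.2 says "then H0 is rejected and the study is considered positive. The enrollment will still continue". The documents do not say whether the interval then reported belongs to the 100 patients or to the 170.

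**The concern.** The plan accepts that interim looks disturb the conventional exact interval, but corrects for them in one branch only. That branch is the first look at which success can be declared. The only earlier look is a futility check at 40 patients, which removes almost no probability from the outcomes at or above 25/100, so there is little to correct.

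The looks have more effect in two other branches. A trial reaching 170 without a crossing has been conditioned on 15 to 24 responders among the first 100. A trial stopped for futility at 100 had already passed the check at 40. In both, the interval is computed as if the sample size had been fixed.

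At stake is the accuracy of the main interval for the primary endpoint in a cohort that SAP 4.1 calls a single-arm pivotal study. It would be reported as an exact 95% interval, which the stopping rules do not deliver at all plausible true rates.

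**Working it through.** **Inputs (SAP 4.2, Table 2 and 13.4; the same rules are in Protocol 9.1).** H0 14.7%, H1 23%.
- 40 patients: "the study enrollment will continue if at least 5 (12.5%) out of 40 patients have response of CR/CRh".
- 100 patients: "If the number of CR/CRh is less than 15 (15%) out of 100 patients, then the study is considered futile and enrollment will be stopped"; success at 25 or more.
- 170 patients: success at 35 or more.

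**Step 1: reproduce the plan's figures.** The binomial paths (40, then 60 more, then 70 more) were enumerated exactly.

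| Quantity | Plan | Recomputed |
|---|---|---|
| Interim alpha | 0.005 | 0.0047 |
| Overall alpha | 0.024 | 0.0047 + 0.0192 = 0.0239 |
| Power at 23% | about 80% | 35.3% + 43.4% = 78.7% |
| Futility stop under H0 | 55% | 28.1% + 26.5% = 54.6% |

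The design is as described.

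**Step 2: the intervals.** The conventional interval is Clopper-Pearson. For the sequential interval, rank all stopping outcomes and solve, for the observed outcome x:
- lower limit: P(outcome ranked at or above x) = 0.025
- upper limit: P(outcome ranked at or below x) = 0.025

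Stage-wise ordering runs from stops at 40, through futility stops at 100 and final counts at 170, to successes at 100; within each group, outcomes are ranked by count.

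| Outcome | Conventional (%) | Stage-wise (%) |
|---|---|---|
| 25/100, interim success | 16.88-34.66 | 16.88-34.67 |
| 35/170 | 14.78-27.45 | 14.75-27.73 |
| 38/170, lower | 16.33 | 15.96 |
| 40/170, lower | 17.37 | 16.49 |
| 42/170, lower | 18.42 | 16.76 |
| 30/170, upper | 24.22 | 25.38 |
| 14/100, futility, upper | 22.37 | 24.39 |
| 10/100, futility, upper | 17.62 | 23.68 |
| 4/40, futility | 2.79-23.66 | 2.79-23.66 |

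Over all interim successes (25/100 and above) the largest difference in either limit is about 0.01 percentage points. At 40/170 the lower limit differs by 17.37 - 16.49 = 0.88 points, and at 14/100 the upper limit differs by 24.39 - 22.37 = 2.02 points. In both 100-patient futility rows the conventional interval excludes the 23% target and the sequential one includes it.

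**Step 3: sensitivity to the ordering.** Ordering by observed rate gives the same limits at 30, 35, 38, 40 and 42 of 170, to two decimals. At 25/100 it gives 16.82-33.22%, so the upper limit moves by 34.66 - 33.22 = 1.44 points.

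**Step 4: coverage of the plan as written.** For each true rate p, sum the probabilities of the outcomes whose reported interval misses p.

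| True rate | Lower limit above p | Upper limit below p | Coverage |
|---|---|---|---|
| 14.7% | 2.4% | 1.5% | 96.2% |
| 16.85% | 3.9% | 1.0% | 95.1% |
| 21% | 2.4% | 3.6% | 94.1% |
| 23% | 2.5% | 3.6% | 93.9% |
| 23.7% | 2.2% | 4.8% | 93.0% |

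The minimum is 92.98%, at 23.7%. The misses there are:
- upper limit: 2.47% (stop at 40) + 0.79% (futility at 100) + 1.53% (final) = 4.79%
- lower limit: 2.20% (success at 100) + 0.03% (final) = 2.23%
- total: 7.02%

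With the sequential interval at every stopping outcome, minimum coverage is 95.03% under either ordering. A fixed 170-patient Clopper-Pearson interval does not fall below 95.0% on the same grid, so the shortfall comes from the looks.

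**Step 5: how often it matters.** At a true 23% the trial succeeds at the final analysis without a crossing 43% of the time and crosses at the interim 35% of the time. It reaches the final analysis with 38 or more responders 27% of the time; at 38 the lower limit is overstated by 16.33 - 15.96 = 0.37 points, and by more at higher counts. A futility stop at 100 has probability 1.2%.

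**The case against.** A reader might infer three stronger things that the documents and the arithmetic do not support.

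**That the final-analysis interval itself covers only 93%.** It does not. The 93.0% belongs to the whole reporting procedure. Given that the trial reaches the final analysis, the conventional interval covers 97.6% at a true 23% and 97.2% at 23.7%. Of the 7.0% non-coverage at 23.7%, 2.47 + 2.20 = 4.67 points arise at stops at 40 and successes at 100, where the stage-wise interval is practically the conventional one. The early stops use up nearly all of the 2.5% allowed for upper-limit misses, and the unadjusted later intervals add to it. At that rate the added misses understate the drug.

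**That the success claim is affected.** No section compares a confidence limit with 14.7%. Success is a count, and its alpha of 0.0239 already accounts for the looks. At 35/170 both lower limits exceed 14.7%. Lower-limit error does reach 3.9% near 16.85%, but two-sided coverage there is still 95.1%.

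**That the planned sequential interval always equals the ordinary one.** This holds under stage-wise ordering. Under ordering by observed rate the 25/100 upper limit changes by 1.4 points, and the plan does not say which ordering it means.

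The strongest remaining argument is that the interval is descriptive and that stage-wise ordering has a price. Its lower limit flattens at high final counts: 45/170 gives 16.87%, just below the 16.88% at 25/100, whereas ordering by observed rate gives 18.53%. That is a reason to choose the ordering deliberately. It does not justify correcting one branch only.

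**Conclusion.** The point holds as a limited defect in interval reporting. The sequential interval is specified where, under stage-wise ordering, it changes almost nothing, and is absent at the final analysis without a crossing and at a futility stop at 100. Typical differences are 0.4 to 1.7 points in the lower limit for 38 to 42 of 170, 1.2 points in the upper limit at 30/170, and 2.0 points in the upper limit at 14/100. Procedure-wide coverage is 93.9% at the target rate and 93.0% at worst. Stops at 40 are unaffected under stage-wise ordering. Boundaries, alpha, power and sample size stand.

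The calculation assumes that the stopping rules are followed as written and that the n = 100 interval is the one reported after a crossing. If the conventional n = 170 interval were reported instead, minimum coverage would be 92.8%. The final-analysis limits quoted do not depend on which of the two orderings is used; the near-identity at 25/100 does.

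**What to change.** In SAP 11.1, Protocol 9.6.1 and the matching synopsis text:

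1. Name the ordering used for the sequential exact interval.
2. Report that interval as the main 95% interval at every stopping outcome: futility stop, interim success and final analysis. Keep the fixed-sample exact interval as descriptive.
3. State that after an interim crossing the main interval is the one at n = 100, and that the 170-patient rate is reported alongside it with a descriptive interval. This matters because at a true 23% the expected observed rate, given a crossing, is 27.5%.

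The cost is a few sentences and a short program. The statistical price is a slightly lower lower limit after success at the final analysis and, under stage-wise ordering, one that flattens near 16.9% for high final counts. The success count of 35/170 does not change: its sequential lower limit is 14.75%.

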11.2 Secondary Efficacy Analyses

Counts, percentages, and two-sided exact 95% confidence intervals will be used to describe categorical secondary variables. Kaplan-Meier (KM) methods will be used to estimate time-to-event endpoints, unless otherwise specified. All secondary efficacy endpoints will be summarized in both efficacy and response evaluable population by PIF, ER, and total.

11.2.1 Key Secondary Efficacy Analyses

The key secondary efficacy endpoints include CR rate, CRh rate, duration of response, postbaseline transfusion independence rate, HSCT rate and incidence and duration of hospitalization.

Duration of response (DOR) will be calculated from the time of initial documentation of response to the time of disease relapse or death due to any cause, whichever occurs first. Patients who are still in response at study completion without alternative therapies will be censored at the time of their last disease assessment.

Duration of response will be calculated for patients who achieve the first evidence of CR or CRh as primary analysis. A separate exploratory analysis will be conducted for patients who achieve the first evidence of complete response (CR, CRh, CRi [CRn, CRp], or MLFS).

DOR (months) = (date of event [disease relapse or death] or date of censoring –date of first evidence of response + 1) / (365.25/12)

Sensitivity analyses will be done for duration of response by using the additional censoring rules below:

- Censored at the date of HSCT.
- Censored at the date of other alternative therapies such as surgery, procedure, radiation and subsequent antileukemic therapy, etc.
- Patients with two or more consecutive missing response assessments prior to event will be censored at the last date of response assessment before the missing assessments.

The duration of response will be analyzed using the KM method. The 25th percentile, median and 75th percentile time (including two-sided 95% CI) will be summarized.

Post-baseline transfusion independence is defined as no transfusion during any consecutive 56-day period on-study. Post-baseline transfusion independence will be summarized for RBC and platelet transfusion separately and in total. Transfusion dependence at baseline is defined as any red blood cell or platelet transfusions during the 28 days prior to the first dose of study drug. The rate of conversion from transfusion dependence to transfusion independence will be calculated. The rate of patients who are transfusion independent at baseline and remain independent during any 56-day post-baseline period will also be calculated.

HSCT rate is defined as rate of successful HSCT through study treatment. Patients who received other therapies (except for conditioning therapy) for AML after discontinuation of study drug and later undergo a subsequent HSCT will not be included. Number and percentage of patients with HSCT will be summarized.

Incidence and Duration of Hospitalization, summaries will be provided for the efficacy population, as well as independently for patients who achieved CR or CRh. Summaries will include duration of initial hospitalization as well as incidence, number and duration of subsequent hospitalizations following the initial discharge, number of days hospitalized, and the reasons for hospitalization.

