## **3.2** Secondary Objectives

- Assessment of CR rate, CRh rate, overall complete response rate (OCRR; CR, CRh, CRi [CRn, CRp], or MLFS), objective response rate (CR, CRh, CRi [CRn, CRp], MLFS, or PR), time to response and duration of response (DOR).
- To measure early mortality rates, overall survival (OS) and event-free survival (EFS).
- To determine the rate of eligible patients, per institution criteria, that transition to successful stem cell transplant after achieving overall complete response (CR, CRh, CRi [CRn, CRp], or MLFS).
- To assess rate of conversion to and maintenance of transfusion independence.
- To evaluate duration of initial hospitalization for flotetuzumab administration.
- To evaluate incidence and duration of hospitalizations subsequent to initial discharge.
- To monitor the safety and tolerability of flotetuzumab.
- To characterize the PK and immunogenicity of flotetuzumab.
- To determine safety and efficacy of tocilizumab in the treatment of IRR/CRS.

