3.2 Secondary Objective(s)

Collectively, the secondary objectives of this study are:

- Assessment of CR rate, CRh rate, overall complete response rate (CR, CRh, CRi [CRn, CRp], or MLFS), objective response rate (CR, CRh, CRi [CRn, CRp], MLFS, or PR), time to response and duration of response (DOR).
- To measure early mortality rates, overall survival (OS) and event-free survival (EFS).
- To determine the rate of eligible patients, per institution criteria, that transition to successful stem cell transplant after achieving complete response (CR, CRh, CRi [CRn, CRp], or MLFS).
- To assess rate of conversion to and maintenance of transfusion independence.
- To evaluate duration of initial hospitalization for flotetuzumab administration.
- To evaluate incidence and duration of hospitalizations subsequent to initial discharge.
- To monitor the safety and tolerability of flotetuzumab.
- To characterize the PK and immunogenicity of flotetuzumab.
- To determine safety and efficacy of tocilizumab in the treatment of IRR/CRS.

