6.2 Secondary Efficacy Endpoints

Key secondary endpoints are listed in Table 3.

Table 3Key Secondary Endpoints

Name	Description
Duration of response (DOR)	Time of initial documentation of response to the time of disease relapse or death due to any cause, whichever occurs first.
Rate of post-baseline transfusion independence	Rate of no transfusion during any consecutive 56-day period on-study.
Rate of HSCT	Rate of successful HSCT through study treatment.
Incidence and duration of hospitalization	Duration of initial hospitalization as well as incidence, number and durations of subsequent hospitalizations following the initial discharge, number of days hospitalized, and reasons for hospitalization.
CR rate	Rate of complete remission.
CRh rate	Rate of complete remission with partial hematologic recovery.

The additional secondary endpoints are listed in Table 4.

Name	Description
Overall complete response rate	Rate of achievement of BM blast of < 5%, CR+CRh+CRi [CRn, CRp]+MLFS according to IWG AML response criteria.
Objective response rate	Rate of CR+CRh+CRi [CRn, CRp]+MLFS+PR according to IWG AML response criteria.
Overall survival (OS)	Time from first dose to death from any cause.
Event-free survival (EFS)	Time from first dose to the date of relapse after CR/CRh/CRi [CRn, CRp], or death from any cause, whichever occurs first.
Time to response (TTR)	Time from first dose to the first CR, CRh, CRi (CRn, CRp), or MLFS.
Mortality rate at 30, 60, 90 and 180 days	Rate of death from any cause within 30, 60, 90, 180 days of first study dose.
Six-month survival rate	Probability of survival at 6 months from first study dose.
One-year survival rate	Probability of survival at 1 year from first study dose.
Immunogenicity	Proportion of patients who become positive for anti-drug antibody production.
Pharmacokinetics	Evaluation of serum concentration of flotetuzumab and its relationships with efficacy, safety and correlative endpoints.

Table 4 Additional Secondary Endpoin	ble 4	Additional Secondary Endpoints
--------------------------------------	-------	--------------------------------

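### The planned HSCT rate requires neither a prior overall complete response nor transplant eligibility, so it does not answer the HSCT objective, which requires both

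*SAP*

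**What the plan says.** **Objective.** Protocol 3.2, also in the Synopsis: "To determine the rate of eligible patients, per institution criteria, that transition to successful stem cell transplant after achieving overall complete response", with that response listed as CR, CRh, CRi (CRn, CRp) or MLFS. SAP 3.2 repeats the objective with the same response list.

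**Endpoint.** SAP Table 3 (Section 6.2) describes it as "Rate of successful HSCT through study treatment". SAP 11.2.1 states: "HSCT rate is defined as rate of successful HSCT through study treatment". Protocol 9.6.2.1 uses the same definition, and both add one restriction, which removes from the count: "Patients who received other therapies (except for conditioning therapy) for AML after discontinuation of study drug and later undergo a subsequent HSCT". The statistic is simple: "Number and percentage of patients with HSCT will be summarized".

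**Denominator.** The HSCT definition names none. The general rule in SAP 11.2 and Protocol 9.6.2 applies: "All secondary efficacy endpoints will be summarized in both efficacy and response evaluable population by PIF, ER, and total".

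**When transplant may happen.** Protocol 4.1 allows transition to transplant throughout induction and consolidation for patients who are eligible at their institution. It sets no response requirement.

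**Data named.** The registration items (Protocol 8.1.2.1) and the follow-up items (Protocol 8.3.2) include treatment history and transplant status, but not transplant eligibility.

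**The concern.** The objective has two conditions: the patient is eligible for transplant, and the transplant follows an overall complete response. The endpoint has neither. If the SAP is followed exactly, the reported rate can include transplants that no overall complete response preceded, and its denominator is not restricted to eligible patients. A reader of the study report would take that figure as the answer to the objective. It would be the answer to a different question: how many treated patients reached transplant without intervening AML therapy.

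**Working it through.** No HSCT rate, target or precision is stated, so there is no figure of the plan to reproduce. The check is a comparison of text, followed by an illustration on assumed counts.

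**Side by side**

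| Element | Objective | HSCT rate as planned |
|---|---|---|
| Event | Successful transplant preceded by CR, CRh, CRi or MLFS | Successful HSCT; no prior response required; HSCT after other AML therapy not counted |
| Denominator | Patients eligible by institution criteria (all of them, or only those in overall complete response: unclear) | Efficacy and response evaluable populations |

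1. *Does anything else supply the response condition?* No. The response evaluable population (SAP 5) requires an assessment, or removal for progression, death or a treatment-related adverse event. It is not a set of responders. The exclusion of HSCT after other AML therapy does not refer to response.
2. *Can a transplant without prior overall complete response occur under the protocol?* Yes. Protocol 4.1 ties transition to eligibility only, and it lists transplant as a reason to end induction separately from reaching CR or CRh.
3. *Where does the missing eligibility condition matter?* Mainly in the denominator, because Protocol 4.1 already makes eligibility a condition of moving to transplant.
4. *Is a responder summary planned elsewhere?* Yes. SAP 11.2.1 summarizes hospitalization separately for CR/CRh patients. It plans nothing similar for HSCT.

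**Illustration (all counts assumed except N = 170, from SAP 4.2)**

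Assume 30% overall complete response, 70% eligibility, half of eligible responders transplanted, and 6 further transplants without prior response.

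- Responders: 0.30 × 170 = 51. Eligible responders: 0.70 × 51 = 35.7, taken as 36. Transplanted after response: 36 / 2 = 18. All eligible patients: 0.70 × 170 = 119.
- Planned rate: (18 + 6)/170 = 14.1% (exact 95% CI 9.3 to 20.3%).
- Prior response required, same population: 18/170 = 10.6% (6.4 to 16.2%).
- Over all responders: 18/51 = 35.3%.
- Objective, read as eligible responders: 18/36 = 50.0% (32.9 to 67.1%).
- Objective, read as all eligible patients: 18/119 = 15.1%.

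The 6 extra transplants move the planned rate from 10.6% to 14.1% and leave both readings of the objective unchanged.

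**Range.** Take response 20 to 40%, eligibility 50 to 100%, half of eligible responders transplanted, and no transplant without response.

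- Planned rate: 8/170 = 4.7% to 34/170 = 20.0%.
- Eligible-responder rate: 8/17 = 47.1% to 26/51 = 51.0%. This is 2.5 times (50.0/20.0) to 10 times (47.1/4.7) the planned rate.
- All-eligible rate: it equals the planned rate divided by the eligible fraction, so it is 1.0 to 2.0 times the planned rate.

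Transplants without response can reverse the direction. With 30% response, everyone eligible and 6 such transplants, the planned rate is (26 + 6)/170 = 18.8%, against 26/170 = 15.3% for the all-eligible reading.

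**The case against.** **The efficacy-population denominator is defensible.** It does not condition on a post-baseline outcome. A rate among responders does, and it gives a larger, more flattering figure. This stands: the planned rate should be kept, and the responder rate should be a supplement.

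**The endpoint is already restricted.** A reader might infer that every transplant counts. The documents do not support that: the HSCT must be successful, and HSCT after other AML therapy is excluded. A patient with persistent disease counts only if transplanted without such therapy, and nothing in the documents says how often that would happen. This limits the concern but supplies neither missing condition.

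**The gap may be small.** A reader might infer that the planned figure must fall several-fold below what the objective asks for. That follows only if the denominator is eligible responders. The objective can equally be read with all eligible patients below the line, and the difference may then be slight.

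**The stakes are limited.** A reader might infer that bridging to transplant is a central claim of benefit. The documents do not say so. HSCT is one of six key secondary endpoints, and Protocol 7.10 names hospitalization and transfusion independence, not HSCT, as support for CR/CRh.

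**Conclusion.** The mismatch holds. The planned HSCT rate lacks the response condition in its numerator and the eligibility condition in its denominator, and no other section supplies them. It therefore does not answer the stated objective.

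The size cannot be given. It depends on three things that the documents do not state: how many transplants occur without prior overall complete response, what fraction of patients is eligible, and which denominator the objective intends. Even the direction is open under the all-eligible reading.

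The documents do not support calling the efficacy-population rate invalid; it answers another question. The endpoint is summarized descriptively with exact confidence intervals and takes no part in the three-stage test, so alpha, power and the primary analysis are untouched.

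**What to change.** In SAP 6.2 and 11.2.1 and Protocol 9.6.2.1:

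- Keep the exclusion of HSCT after other AML therapy, and state the numerator and denominator explicitly.
- Add HSCT after documented CR, CRh, CRi or MLFS, reported over the efficacy population and, as a supplementary rate, over overall complete responders.
- Show transplants without prior overall complete response as a separate count.
- For eligibility, choose one of two routes. Either record institutional eligibility and add the eligible-patient rate, saying whether its denominator is all eligible patients or eligible responders; or reword the objective in Protocol 3.2 (with the Synopsis) and SAP 3.2 to drop the condition.

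The response part costs some SAP and protocol wording and one cross-tabulation. Response dates are already needed for duration of response, and HSCT dates for its sensitivity analysis that censors at transplant. Nothing is lost, because the efficacy-population rate remains. Recording eligibility may need a new eCRF item, since the protocol's registration and follow-up lists do not include it; rewording the objective needs no new data.
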